6.6. Procedures to ensure blinding

This is a double-blind study: neither the patient, nor the investigators will be aware of arm allocation of each study participant. Maintaining double blind design is a known challenge in non-invasive neuromodulation devices trials. Several means are planned to ensure the double-blind aspect of this trial.

	QMS document Nerivio TCH-008 Clinical Study Protocol	Doc ID: TEC0250 Revision #: 3.0 Page: 39 of 58
---	--	--

- Selection of identically looking active and sham devices as control means is only a single step aimed at maintaining blindness.
- Adherence to randomization procedure by clinical staff is critically important.
- Importance of adherence to study design and procedures will be explained to participants during enrollment.
- No information regarding expected stimulation perception will be provided, except for the fact that stimulation intensity adjustment control will allow to adjust intensity to a "strong but not painful" level.
- Before the end of the treatment phase, participants will not be asked directly any questions regarding treatment perception.
- The clinical staff will be instructed to not engage in any discussions regarding anticipated treatment perception.
- Device training will be performed using a training video with minimal contact with the site staff to maintain the blinding.
- The patient will use only the allocated device following the randomization procedure.

To assess blinding, participants will be asked at the end of the treatment phase which group they think they had been assigned to (active, sham, do not know).

6.7. Data management

The data management function will be supported by a cloud-based electronic data capture (EDC) system developed by FlaskData.IO (Modi'in, Israel). FlaskData.IO provides services for collection and remote monitoring of clinical trials data, compliant with HIPAA and 21 CFR Part 11. EDC portals with secure authorized access will be made available to every participating site, as well as to the study monitor.

Data captured by the clinical personnel will be entered directly into pre-specified eCRF screens by the site personnel. Data from paper sources will be entered into the study database. Automatic data checks will be implemented for majority of entry fields to provide opportunity for resolving data inconsistencies as soon as possible to its occurrence. Efforts will be made to identify missing or incorrect data and promptly resolve these issues.

Data collected by the smartphone application will be directed to a secured cloud-based database where it will undergo analysis aimed at detecting of missing data and other inconsistencies. The smartphone will transmit PRO and technical data containing activation times, stimulation intensity and ePRO via the smartphone to a central electronic database for analysis. Activities such as repeatedly aborted programs, missing feedbacks, inconsistent stimulation intensity adjustments, will be communicated to the

	QMS document Nerivio TCH-008 Clinical Study Protocol	Doc ID: TEC0250 Revision #: 3.0 Page: 40 of 58
---	--	--

research coordinator of the corresponding site, using the participants' ID codes. Automated means were developed to identify and provide corresponding notifications regarding events that may lead to protocol deviations and/or missing data, and which resolution may require involvement of study personnel. Examples of such events include missing PRO data or low device battery level. An automated system was implemented to notify the participant, site study coordinator and the sponsor's study monitor of such issues. Missing data will be automatically identified by a script running on the cloud of FlaskData.IO, and queries will be generated to the participants and the corresponding site study coordinator. Near real time detection of problems in accumulating data will allow timely generation and resolution of queries. Intermediate data processing and translation into eCRF format will be performed. Processed data are further pushed into the EDC system.

A daily back-up of the database will be performed. In addition, a copy of each participant's ePROs and other activities will be stored in his/her smartphone memory and can be retrieved if needed.

EDC tools will be used for locking the database and exporting to SAS compatible format for interim and final statistical analyses. Query resolution will also be performed using EDC tools.

All paper-based source data and relevant medical documents that also serve as source documents will be maintained by the sites and will be available as eCRF attachments. participant identification will be removed from all data and the participants will be identified by their codes. The site investigator is responsible for ensuring that eCRFs are filled in a timely manner and that relevant paper documents are properly stored. The investigators will provide the documents to the sponsor either through the sponsor representative or by mail per the sponsor's request.

Access to data will be authorized and controlled, in accordance with relevant regulations and guidelines.

The study will be performed according to the protocol. At each site, the PI will appoint staff member(s) that will be responsible for completing the CRFs supplied by the sponsor.

Specifics of data query handling are given in data management and monitoring plans. Audit trail for data entry and corrections will be maintained.

6.8. Monitoring plan

An independent data monitoring committee (DMC) will be responsible for providing oversight of the data monitoring issues. The DMC will periodically review and evaluate the accumulated data. The DMC will make recommendations regarding enrollment, continuation, modification, or termination of the study. The data reviewed by the DMC will include a summary of the following topics:

- Study progress: subject recruitment, comparison with recruitment targets, retention, protocol adherence, and quality of data collection procedures

	QMS document Nerivio TCH-008 Clinical Study Protocol	Doc ID: TEC0250 Revision #: 3.0 Page: 41 of 58
---	--	--

- Treatment monitoring: data on treatment integrity and adherence
- Safety monitoring: data related to the safety of the subjects, including any adverse events or side effects related to the treatment
- Efficacy monitoring: interim efficacy analysis and recommendations
- Futility monitoring: futility will be assessed during the interim analysis

7. STATISTICAL CONSIDERATIONS

7.1. Study design and aim

The study is designed as a prospective, double-blind, sham-controlled, multicenter study. This study aim is to evaluate the efficacy and safety of Nerivio for the preventive treatment of migraine.

7.2. Endpoints

7.2.1. Primary efficacy endpoint

The primary efficacy endpoint of the study is the difference between the groups in the mean change in the average of migraine headache days per month comparing the 4-week baseline phase (weeks 1 through 4) with the last 28 days (4 weeks) of the treatment phase (weeks 9 through 12). The groups will be compared with the independent t-test.

A migraine headache day is defined as a calendar day with headache that is accompanied by at least one of the following symptoms: aura, photophobia, phonophobia, nausea and/or vomiting; or a calendar day with a headache that is treated with a migraine-specific acute medication.

Subset Analyses

The primary endpoint will also be evaluated stratified by center using a General Linear Model ANOVA test.

A sensitivity analysis of the primary endpoint will be performed to assess the impact of missing data on the study outcome. This will be performed using several possible imputation methods.

Adjustment for other covariates such as demographics or other baseline participant characteristics may be performed by adding these variables into a multivariate linear regression.

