After the enrollment visit, participants will undergo a 4-week baseline phase aimed to collect headache days, medication use, migraine symptoms, and further assess eligibility. Participants will use the app daily to record headache with time of onset, migraine symptoms and medication use. To ensure compliance, the app will send daily reminders/notifications in a pre-specified time in the evening chosen by the participant, but the questionnaire will be available throughout the day. The daily reports will be transferred by the application to the electronic data capture (EDC) system, where they will be collected and registered.

Qualification to enter into the treatment phase: Participants who complete the diary in at least 22 out of the 28 days during the baseline phase (80%), have between 6 to 24 headache days during the 28-day baseline period, at least 4 of their headache days during the baseline phase fulfill the ICHD-3 criteria for migraine (migraine without aura [code 1.1; C and D], or with aura [code 1.2; B and C], or probable migraine, or headaches requiring the use of migraine-specific medications such as triptans, gepants or ergot derivatives) will continue to the treatment phase. Participants who fail these criteria will be excluded from the study and considered screen failure.

Second visit-

Device training: Eligible participants who successfully complete the baseline phase will be randomized in a 1:1 ratio into one of the two groups: either active (treatment with Nerivio active device) or sham group (treatment with Nerivio sham device). During this visit, participants will receive general instructions on study procedures, device mode of operation and warnings/precautions. After the training, patients will be instructed to use the device at home every other day.

The site personnel will be required to document the training session in the CRF. If the visit is conducted remotely, the devices will be shipped/mailed to the participant beforehand, with clear instructions not to open the device before the training.

	QMS document Nerivio TCH-008 Clinical Study Protocol	Doc ID: TEC0250 Revision #: 3.0 Page: 34 of 58
---	--	--

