7.6.5. Treatment by sites interaction

Poolability across centers may be assessed using logistic regression. Centers with less than 10 subjects will be grouped together by geographical area. If the center term is found significant ($p<0.1$), the reason for this interaction will be further explored. This evaluation may include demographic features, symptoms at presentation, clinical and treatment history, and site comparability in the features found to be associated with the primary endpoint variables. Adjustment for other covariates such as demographics or other baseline subject characteristics may be performed by adding these variables into a logistic regression model. The analysis may be repeated for US sites vs. out of US (OUS) sites, if applicable.

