7.7. Randomization

After a subject meets the eligibility criteria, he/she will be equally allocated (with a 1:1 ratio) to one of the following treatment groups based on a randomization scheme with blocks stratified by center:

- Active
- Sham

Subjects will be stratified according to their headache days frequency reported during the baseline phase, to achieve approximately equal numbers of chronic and non-chronic participants. High frequency (HF) group will contain all subjects reported 15 headache days or more, and low frequency (LF) group will contain all subjects reported less than 15 headache days. The stratified randomization will allow a balance in the number of headache days between treatment groups and prevent bias in the mean change of migraine/headache days.

The randomization scheme will be prepared by a biostatistician using a random number generating procedure.

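### The primary t-test on change uses neither baseline migraine days nor the frequency stratum; it is valid, but a pre-specified ANCOVA would be at least about as precise and usually more so

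*Combined protocol and SAP*

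**What the plan says.** Section 7.2.1 defines the primary endpoint as the between-group difference in mean change in monthly migraine headache days, from weeks 1–4 to weeks 9–12. On the test it says: "The groups will be compared with the independent t-test". Section 7.6.3 repeats a two-group comparison at the 5% level in the mITT set and names no covariate.

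Section 7.2.1 offers two further analyses. One is firm: "The primary endpoint will also be evaluated stratified by center using a General Linear Model ANOVA test". The other is optional: "Adjustment for other covariates such as demographics or other baseline participant characteristics may be performed by adding these variables into a multivariate linear regression". Section 7.6.5 adds an optional poolability check, for which "Centers with less than 10 subjects will be grouped together by geographical area".

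Section 7.7 describes allocation as "based on a randomization scheme with blocks stratified by center". It adds: "Subjects will be stratified according to their headache days frequency reported during the baseline phase", with the cut at 15 headache days. It says the stratification will "allow a balance in the number of headache days between treatment groups and prevent bias in the mean change of migraine/headache days".

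**The concern.** The design treats baseline frequency as prognostic, since it stratifies on it to protect the mean change. The primary analysis then ignores it: baseline migraine days enter only by subtraction, and the stratum does not enter at all. The center model does not name either variable. The optional regression could include baseline migraine days, but it leaves open both whether to adjust and for what.

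Two things are at stake. The first is precision. A change score fixes the baseline slope at 1, whereas ANCOVA estimates it and usually leaves less residual variance. The second is pre-specification. An open covariate list permits several versions of an adjusted result, and an unblinded interim look is planned (Section 7.6.7).

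**Working it through.** **Inputs from the plan.** Section 7.4 gives a difference of 2 days, SD 3.0, 117 per arm, two-sided alpha 0.05 and 80% power. Allocation is 1:1 (Section 7.7).

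**Assumed inputs.** The documents give neither the baseline/follow-up correlation r nor the ratio q of follow-up SD to baseline SD. I take r = 0.3, 0.5, 0.7, 0.8, 0.9 and q = 0.8, 1, 1.25. A q above 1 is plausible because participants must "have between 6 to 24 headache days during the 28-day baseline period", while follow-up is not limited.

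**The plan's own figure.** A difference of 2 with SD 3.0 needs 36 to 37 per arm for 80% power, not 117. With 117 per arm, noncentral-t power is 99.9%. The SD that gives 80% power at 117 per arm is 5.44; this value is back-solved and does not appear in the documents.

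**Precision, equal SDs (q = 1).** With s the common SD at each time:
- Change score variance: 2s²(1 − r)
- ANCOVA residual variance: s²(1 − r²)
- Ratio of interval widths: √((1 + r)/2)

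The unadjusted half-width is t(0.975, 232) × 3.0 × √(2/117) = 0.773 days.

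| r | 0.3 | 0.5 | 0.7 | 0.8 | 0.9 |
|---|---|---|---|---|---|
| Width factor | 0.806 | 0.866 | 0.922 | 0.949 | 0.975 |
| ANCOVA half-width (days) | 0.623 | 0.669 | 0.712 | 0.733 | 0.753 |

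**Precision, unequal SDs.** The factor is √(q²(1 − r²)/(1 + q² − 2rq)). It never exceeds 1 and equals 1 when rq = 1.

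| r | 0.3 | 0.5 | 0.7 | 0.8 | 0.9 |
|---|---|---|---|---|---|
| q = 1.25 | 0.886 | 0.945 | 0.990 | 1.000 | 0.975 |
| q = 0.8 | 0.709 | 0.756 | 0.792 | 0.800 | 0.780 |

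**Chance baseline imbalance (q = 1, SD of change 3.0).** The implied baseline SD is 3.0/√(2(1 − r)) = 2.54 to 6.71 for r from 0.3 to 0.9. Under simple randomisation, one standard error of the baseline difference is that SD × √(2/117) = 0.33 to 0.88 days. It shifts the unadjusted estimate by (1 − r) times that amount, 0.23 to 0.09 days; stratification makes the shift smaller. This is the same gain seen another way, because 2(1 − r) = (1 − r²) + (1 − r)².

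**Type I error.** Null simulation: 234 participants, two frequency strata, 10,000 runs, Monte Carlo SE about 0.22 points. Assumed: blocks of 4, normal counts, correlation 0.9 between the headache-day and migraine-day baselines.

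| r | 0.3 | 0.5 | 0.7 | 0.8 | 0.9 |
|---|---|---|---|---|---|
| t-test, q = 1 | 2.9% | 3.5% | 4.1% | 4.4% | 4.7% |
| t-test, q = 1.25 | 3.9% | 4.2% | 5.0% | 4.7% | 4.7% |
| t-test, q = 0.8 | 2.4% | 2.6% | 2.9% | 3.0% | 3.2% |

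ANCOVA with baseline and stratum stayed between 4.7% and 5.4%. The t-test is therefore valid, and conservative where the stratum predicts change.

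**Power.** At SD 3.0 it is at least 99.9% either way. At SD 5.44 with q = 1, the noncentral t gives 80% unadjusted, against 94 / 90 / 86 / 84 / 82% with ANCOVA for r = 0.3 / 0.5 / 0.7 / 0.8 / 0.9.

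**The full model.** The figures above are for baseline adjustment, plus the stratum in the type I error check. The number of centers is not stated. A simulation of the model with baseline, stratum and 15 assumed centers unrelated to outcome gave intervals about 1.5% wider than baseline-only ANCOVA (234 analysed of 360 with random loss, SD 5.44, 3,000 runs). With equal SDs they were still 1% to 18% narrower than the t-test's. At q = 1.25 the half-widths were 1.408 against 1.399 days for the t-test at r = 0.7, and 1.423 against 1.401 at r = 0.8, so at worst about 1.6% wider.

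**The case against.** The strongest reply is that nothing is broken. The t-test is valid and tests the hypothesis in Section 7.3. On the plan's inputs the gain is 0.02 to 0.15 days of half-width against a 2-day target, which would alter no conclusion. That stands, and it is why this is an improvement and not an error.

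Several narrower points also stand:
- The 80% starting power ignores stratified randomisation. In a simulation that includes it (SD of change 5.43), t-test against ANCOVA power was 83 v 94, 81 v 89, 81 v 86 and 81 v 83% for r = 0.3, 0.5, 0.7 and 0.9. The gain is then 2 to 11 points, not 2 to 14.
- Adding the stratum to baseline days changed power by under 0.2 points, so most of the benefit comes from baseline migraine days.
- Uninformative center terms cost a little precision, so the full model is almost free rather than strictly free.

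Two points carry less weight. The optional regression does not fill the gap, because it is discretionary and names neither variable. Section 9.1 mentions a statistical analysis plan kept separately, which might name covariates, but that would not change the primary test stated in this protocol.

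**Conclusion.** The concern holds. The primary test omits both baseline migraine days and the frequency stratum, and no analysis in the document names either. The t-test controls type I error, so the issue is efficiency and pre-specification.

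With equal SDs and r from 0.3 to 0.9, baseline adjustment narrows the interval by 19% to 2.5%. If follow-up SD is 1.25 times baseline SD, the narrowing is 11% and 5.5% at r = 0.3 and 0.5, and between nothing and 2.5% at r of 0.7 or more. At a ratio of 0.8 it is 20% to 29%. All of this rests on assumed r and SD ratios. A material power gain further requires a true SD near 5.4, which the plan does not state.

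Adjustment does not address selection into the mITT set, which depends on diary completion and treatments after randomisation. The stratum is defined on headache days and the endpoint on migraine headache days, so the two covariates are related but not interchangeable.

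**What to change.** In Section 7.2.1, make the primary analysis an ANCOVA on change or on weeks 9–12 migraine days; with baseline as a covariate, the treatment estimate is the same. Include treatment, baseline monthly migraine days, frequency stratum (15 or more against fewer than 15 headache days) and center, with small centers pooled as in Section 7.6.5. Keep the t-test as a sensitivity analysis. Fix the model before the unblinded interim look; the documents do not show whether that look has taken place.

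The cost is a wording change, possibly an amendment needing IRB/EC approval (Section 9.1), and matching text in any separate analysis plan. Section 7.4 has no ANCOVA basis, and the interim threshold in Section 7.6.7 is a difference in mean reduction. The amendment should therefore say which estimate each of them uses. Baseline migraine days, stratum and center are already collected.

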7.2.2. Secondary efficacy endpoints

Secondary efficacy endpoints include:

	QMS document Nerivio TCH-008 Clinical Study Protocol	Doc ID: TEC0250 Revision #: 3.0 Page: 42 of 58
--	--	--

1. Difference between treatment groups of mean change in the average number of moderate/severe headache days per month comparing the 4-week baseline phase (weeks 1 through 4) with the last 28 days of the treatment phase (weeks 9 through 12).
A moderate/severe headache day is defined as a calendar day with moderate or severe headache.
2. Difference between treatment groups in the mean change in the average number of headache days per month in comparing the 4-week baseline phase (weeks 1 through 4) with the last 4 weeks of the treatment phase (weeks 9 through 12). A headache day is defined as a calendar day with headache (at any severity).
3. Difference between treatment groups in the achievement of at least 50% reduction from baseline in the mean number of moderate to severe headache days per month in the last 4 weeks of the treatment phase (weeks 9 through 12).
4. Difference between treatment groups in the the mean change from baseline in the HIT-6 total score.
5. Difference between treatment groups of the mean change from baseline in the MSQ role function.

The secondary efficacy variables will be summarized by a count and percentage and compared with a chi-squared test or a Fisher's exact test.

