3. IDENTIFICATION AND DESCRIPTION OF THE DEVICE INFORMATION

3.1. Intended use

Current indication for use of the device:

The Nerivio is indicated for acute treatment of migraine with or without aura in patients 18 years of age or older. It is a prescription use, self-administered device for use in the home environment at the onset of migraine headache or aura.

This study aims to expand the current indication to include the preventive treatment of migraine in patients 18 years of age or older.

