7.4. Sample size

A sample size of 234 participants, 117 per each treatment arm, was determined to provide 80% power to detect a mean ($\pm SD$) difference of 2 ± 3.0 in the reduction in number of migraine headache days from the baseline to weeks 9-12 of the treatment phase, between the active group and the sham group at a two-sided alpha level of 0.05. With an anticipated discontinuation rate of about 35%, up to 375 participants are planned to be enrolled. In case of higher dropout or non-eligible participants or missing data, enrollment may be extended in order to reach the desired sample size.

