7.6. Statistical analysis

7.6.1. General considerations

Statistical analyses will be performed using a statistical software such as SAS® (SAS Institute, Cary NC, USA), or SPSS statistic program version 27.0 (or higher) software. Baseline demographic and other baseline characteristics, together with safety analyses will be performed on all participants who were randomized. Baseline values are defined as the last valid value prior to treatment.

Where confidence limits are appropriate, a two-sided 95% confidence interval will be constructed.

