7.6.3. Efficacy analysis

The efficacy endpoints will be assessed on evaluable reports of daily symptoms.

A modified intent to treat analysis set (mITT) will include all ITT participants who had at least 22 days of efficacy assessments in the last 4 weeks of the treatment phase (weeks 9 through 12) and at least 12 treatments performed in the last 4 weeks of the treatment phase (weeks 9 through 12). The efficacy analyses will be conducted on the mITT analysis set. The mITT will be assessed for the mean change in migraine days from the 4-week baseline phase (weeks 1 through 4) to the last 4 weeks of the treatment phase (weeks 9 through 12) and will be compared between treatment groups with a significance level $p<0.05$.

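### Five secondary endpoints are to be tested with no order, gate or adjustment; at an inferred 0.05 each, five true nulls give a 10% to 23% chance of a nominally significant result

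*Combined protocol and SAP*

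**What the plan says.** Section 7.2.2 begins "Secondary efficacy endpoints include" and numbers five items, each a difference between treatment groups:

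1. change in moderate/severe headache days;
2. change in headache days of any severity;
3. a 50% responder rate;
4. change in HIT-6 total score;
5. the last item, "Difference between treatment groups of the mean change from baseline in the MSQ role function".

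One closing sentence covers all five: they will be summarised as counts and percentages and "compared with a chi-squared test or a Fisher's exact test". The Synopsis and section 6.4.2 list the endpoints in the same order. Section 7.2.3 keeps a separate exploratory tier.

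The significance level is written for the primary only. Section 7.4 sizes the trial for a difference in migraine headache days "between the active group and the sham group at a two-sided alpha level of 0.05". In section 7.6.3, the sentence containing "will be compared between treatment groups with a significance level" has the mean change in migraine days as its subject. Section 7.6.1 adds that, where confidence limits are appropriate, "a two-sided 95% confidence interval will be constructed".

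Section 3.1 gives the regulatory purpose: "This study aims to expand the current indication to include the preventive treatment of migraine in patients 18 years of age or older".

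**The concern.** The secondaries stand above the exploratory tier and are to be formally compared, so a reader of the final report will take their p-values as evidence. With five comparisons and no rule linking them to the primary or to each other, a nominally significant result is easier to obtain by chance than its p-value suggests. In a trial run to widen an indication, secondary results are natural candidates for supporting statements about benefit. The plan does not tell the sponsor or a regulator which of them could carry such a statement. The primary test itself is not affected.

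**Working it through.** **The plan's own figure.** There is none: no family-wise error rate is given for the secondaries.

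**Inputs.**
- Number of tests: 5 (section 7.2.2).
- Level per test: two-sided 0.05. This is inferred. It is stated for the primary (7.4, 7.6.3), is consistent with the general 95% intervals (7.6.1), and no other level appears.
- True state: all five null hypotheses hold.
- Correlation between the five test statistics: not in the documents. A common value ρ is assumed and varied from 0 to 0.9. It should be positive, because moderate/severe days are a subset of headache days and endpoint 3 dichotomises a day count that is already tested.
- Each endpoint is assumed to get a test that suits it, with an approximately normal statistic.

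**Independent tests.**
- Either direction: 1 − 0.95^5 = 0.226.
- False benefit only (2.5% per test): 1 − 0.975^5 = 0.119.

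**Correlated tests.** With c = 1.96, Φ and φ the standard normal distribution and density functions, and common correlation ρ:

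P(at least one) = 1 − ∫ [Φ((c − √ρ·u)/√(1−ρ)) − Φ((−c − √ρ·u)/√(1−ρ))]^5 φ(u) du.

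For false benefit only, the second Φ term is dropped. Numerical integration gives:

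| ρ | Either direction | False benefit only |
|---|---|---|
| 0 | 22.6% | 11.9% |
| 0.3 | 20.9% | 10.5% |
| 0.5 | 18.3% | 9.1% |
| 0.7 | 14.8% | 7.4% |
| 0.8 | 12.7% | 6.4% |
| 0.9 | 10.2% | 5.1% |

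A single test would give 5% and 2.5%.

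**A more realistic structure.** Simulation treated the three day-based endpoints as one block and the two questionnaires as another, with correlations of 0.5 to 0.8 within blocks and 0.2 to 0.5 between them. The either-direction figure was 15.4% to 20.1%.

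**Would a gate on the primary be enough?** No. If the primary null is also true, requiring a significant primary first cuts the error to about 1% (ρ = 0) to 4% (ρ = 0.8). If the primary effect is real and the gate nearly always opens, the five tests behind it carry almost the full error in the table.

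**Does a fixed sequence work?** Yes. Take the first true null in the order primary, 1, 2, 3, 4, 5. No false rejection can occur unless that one is rejected, and it is tested at 0.05. The family-wise error is therefore at most 5% whatever the correlation. Bonferroni among the five behind the same gate also works: 0.05/5 = 0.01 each, and 1 − 0.99^5 = 4.9% if independent.

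**Can the listed order be used today?** No, for two reasons. Endpoint 3 counts all headache days in the Synopsis and section 6.4.2, but moderate to severe days in section 7.2.2. If both versions were tested there would be six tests: 1 − 0.95^6 = 26.5% if independent. Also, the one named test family suits proportions, whereas endpoints 1, 2, 4 and 5 are mean changes.

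**The case against.** A reader might infer that, as written, any secondary with p below 0.05 counts as success even when the primary fails. The documents do not support that. Section 5.2 says the study hypothesis will be demonstrated by the difference in monthly migraine days, section 7.3 states one null and one alternative for that endpoint alone, and no success rule is attached to any secondary. Nor does section 3.1 say that the wider indication would rest on secondaries. What remains is a gap: nothing says whether the secondaries are confirmatory or descriptive.

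The size can also be challenged:
- The 0.05 per secondary is inferred, and the level in section 7.6.3 belongs to the primary.
- The top of the range needs independence, which overlapping day counts make implausible.
- The figure counts errors in both directions; false benefit alone is half as large or slightly more.
- Fisher's exact test, if used, is conservative and would lower the result somewhat.

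All four points stand and are built into the range. Even at ρ = 0.9 the error is about twice that of a single test.

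Finally, section 9.1 refers to a statistical analysis plan held outside the protocol. A rule might exist there, so its absence is shown only for the combined document. Section 9.1 also lets that plan change without a protocol amendment, which is a reason to put the rule in section 7.2.2 as well.

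**Conclusion.** The concern holds in a limited form. Five secondary comparisons are planned with no order, gate, adjustment or descriptive status. On an inferred two-sided 0.05 per test with all five nulls true, the chance of at least one nominally significant secondary is about 10% to 23% over assumed common correlations of 0.9 to 0. For false benefit alone it is about 5% to 12%, roughly two to five times the 2.5% of one test. The plan does not let a secondary stand in for a failed primary, but it also does not prevent a nominally significant secondary from being presented as a finding. The change should be made; it does not alter the primary analysis.

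**What to change.** Make two changes, in this order, before anyone sees unblinded interim data.

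1. Define endpoint 3 the same way in the Synopsis, 6.4.2 and 7.2.2. Replace the single test sentence in 7.2.2 with a named test for each endpoint: a comparison of means for endpoints 1, 2, 4 and 5, and chi-squared or Fisher's exact for endpoint 3.
2. State in 7.2.2, and in any separate SAP, that the primary is tested at two-sided 0.05. Only if it is significant are secondaries 1 to 5 tested in the listed order, each at two-sided 0.05, stopping at the first p of 0.05 or more. Everything after that point is reported as descriptive.

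This keeps the family-wise error over the primary and secondaries at 5% or less with no loss of power for the primary, provided the interim is used only for futility. That condition should be written down. Section 7.6.7 describes a futility threshold, but section 6.8 lists an interim efficacy analysis and section 7.6.7.2 allows modification of the sample size.

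The cost is a short paragraph and the reconciliation of endpoint 3. The downside is that an endpoint listed after a non-significant one cannot be claimed, however small its p-value. If the sponsor does not want to depend on the order, Bonferroni at 0.01 each behind the same gate is an alternative, at the price of a stricter level for every secondary.
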